### **1.1.1 Reimbursement for travel, parking and meals**

Transportation with Lyft will be arranged for participants who have a car seat for the final study visit (Study Visit 5) through CHOP's Family and Visitor services. In the event that the participant does not have a car seat, the participant will be reimbursed on their ClinCard for their roundtrip travel based on mileage.

### **9.6.1 Payments to parent for time and inconvenience (i.e. compensation)**

Participants will be paid up to a total of \$200 for their participation. They will receive \$40 upon completion of the initial study visit (Baseline). They will then receive \$20 upon completion of each of the three follow-up visits (3 month, 6 month, and 9 month follow-up). At the final study visit (12 month follow-up) they will receive \$100. Participants in the sub-study will receive an additional \$20 payment for completing the sub-study REDCap survey, and an additional \$30 payment for completing the sub-study telephone interview if they are selected to do so. All payments will be made in the form of pre-paid, CHOP-issued debit cards (i.e., ClinCard). In the event that the Enrollment Visit or other follow-up visits are unable to be completed in-person (due to COVID-19 or other reasons), the participant will be mailed a ClinCard. Once study staff confirms that the participant has received the ClinCard, the ClinCard will be activated and relevant payments will be uploaded.

Participants in Phase 1 of the Trauma-Informed Co-parenting Sub-Study will receive a one-time payment of \$20 for participating in the Delphi process. Participants in Phase 2 of the Sub-study will receive a one-time payment of \$20 for participating in an interview. All payments will be made in the form of pre-paid, CHOP-issued debit cards.

### **9.6.2 Gifts**

No other gifts will be given.

## **10 PUBLICATION**

This study will be registered with ClinicalTrials.gov following IRB approval of the final protocol and before any potential patients and their families are enrolled in the study. All study data will then be reported to the ClinicalTrials.gov site. Additionally, all arising publications of Study data and analyses will follow the set of guidelines outlined in the CHOP publications policy manual.

The research team plans to work closely with key stakeholders to disseminate and

implement the findings of the research study into accessible and usable formats in research, clinical, and community-based settings. We will target findings to state and national policymakers, county EI agencies across the state, parent advocacy groups, and pediatric practices using social media, policy briefs, mass emails, and newsletters. We will work with PolicyLab at CHOP to develop dissemination plans. PolicyLab has extensive experience distilling research findings into policy-relevant summaries and disseminating research findings to end-users. We will also utilize traditional approaches such as peer-reviewed publications and presentations at national meetings to disseminate findings to other researchers.

**APPENDIX**

See attached.

---

ODEI Study Statistical Analyses Plan

Title: The Opening Doors to Early Intervention Study (ODEI)

NCT Number: NCT03625115

Document Date: July 3rd, 2024

ODEI Study Statistical Analyses Plan

Aim 1: To test the effectiveness of the Opening Doors to Early Intervention Program on EI service use and child developmental status among poor minority children residing in an urban community.

- a. *Hypothesis 1a:* A greater proportion of children who are randomized to the intervention will complete EI referrals than children in the control condition at 12 months.

Analysis: Chi square analysis on the difference in completion of MDE by study arm and logistic regression on the difference in MDE completion by arm, controlling for sex, age, and primary care site.

- b. *Hypothesis 1b:* Among children eligible for EI services, children randomized to the intervention will initiate EI services at a greater rate & receiving a longer duration of EI services than children in the control condition.

Analysis: Chi square test on the difference in EI service initiation by arm and logistic regression, controlled for sex, age, and primary care site. Survival analysis with a Kaplan-Meier curve of EI duration of services by arm.

- c. *Hypothesis 1c:* As a result, children who are randomized to the intervention will have more favorable developmental outcomes than children in the control condition at 12 months.

Analysis: Logistic regressions to determine the difference in cognitive and language BSID III scores by arm, controlling for sex, age, and primary care site.

Variable Definitions:

- Completion of EI Referrals: Completion of Multidisciplinary Evaluation (MDE)
- Initiating EI services: Date of first early intervention service
- Duration of EI services: The time between the EI service initiation and discharge from early intervention OR 12 months from randomization (if discharge date is unavailable)
- Developmental outcomes: Language and cognitive composite scores from BSID III assessment.

Aim 2: To assess whether parent engagement mediates the effects of the Opening Doors to Early Intervention Program.

- a. *Hypothesis 2a:* Parent engagement will mediate the association between program participation and completion of EI referrals and participation in EI services (duration).

Analysis: Test the association between study arm at 3 months and EI referral completion and the association between EI parent engagement at 3 months (mediator) and EI referral completion. If both associations are significant, complete a mediation analysis of the association between study arm and completion of EI referrals, mediated by parent EI engagement.

- b. *Hypothesis 2b:* Completion of EI referrals and participation in EI services (dosage) will mediate the association between program participation (duration), parent engagement, and child developmental status

Analysis of EI referral completion and child development status: Test the association between EI engagement at 3 months and Bayley language & cognitive T scores and the association between MDE completion (mediator) and EI engagement at 3 months. If both associations are significant, complete a mediation analysis of the association between EI engagement at 3 months and Bayley language and cognitive T scores, mediated by EI referral completion.

Analysis of program participation and child development scores: Test the association between program participation and Bayley language & cognitive T scores and the association between referral completion (mediator) and program participation. If both associations are significant,

ODEI Study Statistical Analyses Plan

complete a mediation analysis of the association between program duration and Bayley language and cognitive T scores, mediated by referral completion.

Variable Definitions:

- Program participation: participation in ODEI intervention
- Completion of EI Referrals: Completion of Multidisciplinary Evaluation (MDE)
- Initiating EI services: Date of first early intervention service
- Duration of EI services: The time between the EI service initiation and discharge from early intervention OR 12 months from randomization (if discharge date is unavailable)
- Developmental outcomes: Language and cognitive composite scores from BSID III assessment.
- Parent engagement: total score from 2 subscales on parent engagement (Buy-In/Receptivity to EI and Advocacy/Navigating the EI Process)

Aim 3: To explore whether the home learning environment, parental health literacy, or poverty moderate the effects of the Opening Doors to Early Intervention Program on child developmental status.

a. *Aim 3a:* To explore whether differences in developmental scores between intervention and control groups varies by the richness of home learning environment

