## 1.5 Relevant Literature and Data

Child Find services are a mandated component of Part C of the Individuals with Disabilities Education Act to identify and enroll eligible children with developmental delays and disabilities. Child Find practices utilized by EI agencies may employ a variety of different strategies ranging from public awareness campaigns to developmental screening to childcare and clinician referrals. In previous studies, we found that only 50% of urban patients in Philadelphia completed EI referrals once they were identified as having delays and referred using these strategies (See Preliminary Studies section). However, none of these current practices seek to engage, inform, and assist parents to overcome motivational, knowledge, and practical barriers to completion of referrals.

This application is innovative, in our opinion, in adapting a PN model to address poor EI referral and service completion. This model termed “Opening Doors to Early Intervention” was based on a review of the literature of patient navigators (or family navigators, as we will refer to them in our study) and received practical input from practicing clinicians, EI staff, and parents to adapt it. The intervention was manualized to ensure consistency of procedures and included multiple modules addressing 1) education of families regarding knowledge of early child development, 2) information on the EI system and steps necessary to complete an EI referral, 3) brief motivation interviewing to assess families’ goals and treatment preferences and level of interest in initiating EI referrals, 4) assistance with overcoming barriers to completing EI referrals and maintaining EI enrollment, and 5) social work referral in the event of medical complexity or family crisis (See Appendix for Manual of Operations). PNs met with families soon after a referral was made and then followed up with families using phone, email, or text messaging to track completion of the referral steps leading to a multidisciplinary evaluation for services (Fig 3). PNs provided assistance and encouragement when families experienced barriers to the completion of steps. Although the referral steps shown here are county-specific, we retained flexibility in the manual to allow adaptation to counties with different referral processes and steps.

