The study research materials will consist of parent- and observer-reported instruments and EI data. Following written informed consent (which is either completed in person or remotely with the electronic REDCap e-consent process), participant caregivers will complete a baseline visit. Measures of demographic characteristics (child age, sex, race/ethnicity, family income, maternal education level, spoken language, and family structure) (Appendix 2), parental health literacy (SAHL) (Appendix 3), and the home learning environment (StimQ) (Appendix 4) will be collected at this visit. Due to the interactive nature of the SAHL measure, in the event that the baseline visit is conducted remotely, the participant will have the option of either completing the measure of parental health literacy (SAHL) remotely by utilizing a video conferencing application or completing the SAHL in-person at a later date. If a visit is conducted using a video conferencing application, we will try to use a HIPAA-compliant application licensed by CHOP (i.e., Skype, Bluejeans or WebEx). Measures of parent engagement and EI referral and service use will be collected at follow-up visits at 3, 6, 9, and 12 months. These visits will be conducted in-person, by telephone, or by email at the preference of the parent. Parents will be asked at study visits to complete the EI Engagement questionnaire, which was adapted from the CECPS and generated during a prior study (IRB 18-014884), and measures of completion of EI referrals (intake, registration, assignment of service coordinator, home visit, and MDE), eligibility for and initiation of EI services (IFSP), EI services use if eligible (number of EI service visits and whether services were completed or terminated), and use of other services (transfer to Preschool EI services, childcare or preschool enrollment). We will corroborate parent-reported visits with EI staff. Participants will also complete the Philadelphia Expanded ACE measure at one time-point throughout the study. This time-point will typically be the 3-month survey, however the measure may be administered during either the 6- 9- or 12-month follow-up survey time-points in the event that the survey is not completed during the 3-month time-point. The ACEs survey assesses for adverse events in that have already occurred in the past (i.e., childhood adverse experiences),

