## 6.2 Secondary Endpoints

Secondary outcomes include the Bayley-III language, motor, and socioemotional subscales and the binary outcomes of whether patients complete EI referrals and services at 12 months.

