##### Secondary outcomes

Secondary outcomes include the Bayley-III language, motor, and socioemotional subscales and the binary outcomes of whether patients complete EI referrals and services at 12 months. Descriptive statistics for demographic, behavioral, and environmental characteristics measured at baseline will be examined across the two treatment groups to assess the success of the randomization. The secondary outcomes can be modeled using either a linear or logistics mixed effects model, which has similar flexibility. As a secondary analysis, we will examine differences in dosage (duration of EI service use and number of EI service visits) between intervention groups among those eligible for services. We will also examine the impact of public policy changes on the proportion eligible for EI and on the number of service visits pre- and post-change. In addition, we will examine the effects of the intervention by race/ethnicity group, sex, and age group (<18 months, >18 months) to assess for differential intervention effects.

---

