## 7 STUDY INTERVENTION

### 7.1 Main RCT

#### 7.1.1 Description

With the implementation of the intervention, a modified FN model, the FNs will partner with families, engage them in the early intervention program, and provide ongoing communication with families, clinicians, and EI staff. Using data captured in the medical record, the FN will either meet with or speak with families remotely at the beginning of the study to review results of developmental screening tests and/or milestone assessments. This modified FN model process proceeds in five modules. Specifically, they will provide to families 1) education regarding knowledge of early child development, 2) information on the EI system and steps necessary to complete an EI referral, 3) brief motivation interviewing to assess families' goals and treatment preferences and level of interest in initiating EI referrals, 4) ongoing assistance to overcome barriers to completing EI referrals and maintaining EI enrollment, and 5) social work referrals in the event of family crisis or medical complexity. Specific procedures in separate modules, e.g. Early Intervention Intake Monitoring, have been manualized. The FN will contact families weekly to monthly by phone, text messaging, or email depending on family preference to monitor initiation and completion of referral steps, identify family concerns and/or barriers to referral completion, and assist families with problem-solving to identify barriers and solutions to complete EI referrals. Using email or telephone, the FN will also communicate with pediatric clinicians and EI staff to clarify treatment plans and goals and address emerging issues. A fidelity checklist developed in the pilot study will be utilized to assess self-reported task completion by the FN (0- not completed, 1- partially completed, 2- fully completed). In addition, the FN will summarize patient encounters, e.g. telephone calls with parents, in a log file. In the control arm, eligible children and their families will follow usual care procedures. As such, families are counseled by their clinicians, provided with educational handouts on development and the EI process, and referred to EI using electronic faxes from the clinic offices to the EI administrative office. EI staff then contact families by phone to initiate the EI referral process and arrange visits to complete the intake and evaluation (see Fig. 3). Families that fail to complete EI referrals and/or services in a timely manner may be dropped by EI but can be re-referred by their clinicians to complete the process later.

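### SAP Hypothesis 1b compares EI initiation among eligible children, and duration in effect among starters; both groups form after randomisation, and as worded no all-randomised analysis of either outcome is planned

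*SAP*

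**What the plan says.** SAP, Aim 1, Hypothesis 1b: "Among children eligible for EI services, children randomized to the intervention will initiate EI services at a greater rate". The analysis sentence beneath it specifies a chi-square test and a logistic regression (sex, age, site) by arm but names no denominator, so the hypothesis supplies it. The SAP does not define eligibility for EI.

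For duration the SAP plans "Survival analysis with a Kaplan-Meier curve of EI duration of services by arm" and defines duration as "The time between the EI service initiation and discharge from early intervention OR 12 months from randomization (if discharge date is unavailable". Nothing says what value a child who never starts receives.

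Protocol 3.1.1 lists the items collected at the follow-up visits in this order: "completion of EI referrals (intake, registration, assignment of service coordinator, home visit, and MDE), eligibility for and initiation of EI services (IFSP". Protocol 5.1.2.1 gives the same order. Arm is assigned at enrolment (Protocol 3.2).

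Other planned analyses come close. SAP Hypothesis 1a tests completion of the multidisciplinary evaluation (MDE) without an eligibility restriction. Protocol 6.2 lists "the binary outcomes of whether patients complete EI referrals and services at 12 months" among the secondary endpoints, also unrestricted. Protocol 6.4.2.1 adds, as a secondary analysis, "differences in dosage (duration of EI service use and number of EI service visits) between intervention groups among those eligible for services". Protocol 6.3 keeps the as-randomised approach as the primary basis for significance testing in general.

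**The concern.** A comparison between arms is protected by randomisation only if the children compared are those who were randomised, or a subset that arm cannot alter. Children found eligible for EI are not such a subset. The referral steps come first, and Protocol 1.5 describes navigators following families up to "track completion of the referral steps leading to a multidisciplinary evaluation for services". That eligibility is settled at the MDE is an inference from the order of the steps; no sentence says so. The navigator's tasks include "ongoing assistance to overcome barriers to completing EI referrals and maintaining EI enrollment" (Protocol 7.1.1), and Hypothesis 1a predicts that MDE completion will differ by arm. The trial therefore expects its own intervention to change who enters the 1b comparison.

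Duration is selected twice, first through eligibility and then through starting, because its clock does not begin until the first service.

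EI service use is part of Aim 1 (Protocol 2.1), and 1b holds the SAP's between-arm tests of initiation and duration. A difference there, or the lack of one, could reflect which families became eligible or started rather than what navigation did for them. Adjusting for sex, age and site does not remove selection on family characteristics outside those three.

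**Working it through.** **Plan figures.** The documents give no rate of eligibility, initiation or duration, and no power for either outcome, so there is no figure to reproduce. What follows is an illustration.

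**Inputs**
- Randomised: 360, 1:1, so 180 per arm (Protocol 3.2).
- MDE completion: p0 = 50%, p1 = 80%. Assumed. Protocol 1.5 reports 50% referral completion in earlier studies; Protocol 6.5 uses 50% v 80%, but for EI enrolment.
- Eligible once evaluated: e = 60% to 90% in every group. Assumed.
- Every family evaluated under usual care would also be evaluated with a navigator. Assumed, relaxed below.
- No direct navigator effect on starting once eligible. Assumed, so any eligible-only difference is selection.
- s_o is the start rate in families evaluated under either arm (others); s_a is the rate in families evaluated only because of the navigator (added). Assumed.

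**Formulas**
- Eligible-only: control = s_o; intervention = [p0·s_o + (p1 - p0)·s_a] / p1. The difference is (1 - p0/p1)(s_a - s_o), and e cancels.
- All randomised: control = e·p0·s_o; intervention = e·[p0·s_o + (p1 - p0)·s_a]. The difference is e·(p1 - p0)·s_a.

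**Results for initiation**
- A, s_o = 90%, s_a = 60%: eligible-only 90% v (0.45 + 0.18)/0.80 = 78.75%, or -11 points. All randomised: 27.0% v 37.8% (+11) at e = 60%, to 40.5% v 56.7% (+16) at e = 90%.
- B, s_o = 60%, s_a = 90%: eligible-only 60% v (0.30 + 0.27)/0.80 = 71.25%, or +11 points. All randomised: 18.0% v 34.2% (+16) to 27.0% v 51.3% (+24).
- C, both 90%: eligible-only difference 0. All randomised: 27.0% v 43.2% (+16) to 40.5% v 64.8% (+24).

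**Sensitivity.** The bias weight 1 - p0/p1 is 0.375 at p1 = 80% and 0.167 at p1 = 60%. For start-rate differences of 10, 20 and 30 points, the eligible-only bias is 3.8, 7.5 and 11.3 points at p1 = 80%, and 1.7, 3.3 and 5.0 at p1 = 60%. If 5-10% of children would be evaluated under usual care only, the 11 points in A become 9.0 (10% of children, starting at 60%: 84% v 75%) to 15.0 (10%, starting at 90%: 90% v 75%).

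**Against sampling error.** The eligible groups number 180·0.5·e v 180·0.8·e, that is 54 v 86 (e = 60%) to 81 v 130 (e = 90%). The 95% margin for A at e = 60% is 1.96·√(0.09/54 + 0.1673/86.4) = 0.118; at e = 90% it is 1.96·√(0.09/81 + 0.1673/129.6) = 0.096. For B, replacing the numerators by 0.24 and 0.2048 gives 0.162 and 0.132. The assumed bias is about the size of the margin in A and below it in B.

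**Duration, scenario A.** Assume 7 months of service for other families who start and 4 for added families. Starters: 7.0 v (0.45·7 + 0.18·4)/0.63 = 3.87/0.63 = 6.1 months. All randomised, with zero for non-starters: e·3.15 v e·3.87, or 1.9 v 2.3 months (e = 60%) to 2.8 v 3.5 (e = 90%). The sign reverses.

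**The case against.** The strongest defence is that 1b asks a sensible conditional question. A child found ineligible cannot start services, Hypothesis 1a already tests the step most exposed to navigation without restriction, and an all-randomised initiation outcome partly repeats 1a. That stands as a reason to keep the eligible-only result. It does not make that result a randomised comparison, and 1a says nothing about starting or staying in services.

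The initiation analysis sentence carries no restriction, and Protocol 6.3 favours the as-randomised approach, so it could be read as covering everyone. The hypothesis it serves is restricted, however, and no text applies the general statement to initiation or duration. The unrestricted service outcome in Protocol 6.2 concerns completing services, and the SAP does not carry that part forward.

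A reader might infer several stronger things that the documents do not support:
- That the SAP departs from the Protocol. For duration it follows it: Protocol 6.4.2.1 also limits dosage to eligible children.
- That listed secondary endpoints are compromised. Initiation and duration are not among those in Protocol 6.2. Initiation is collected data and a SAP Aim 1 hypothesis; duration is a Protocol secondary analysis.
- That 1b is known to be biased, or biased against the navigator. The direction depends on start rates the documents do not give.
- That the all-randomised effect would approach the full 30-point gap in Protocol 6.5. Those are enrolment rates, and treating them as entry to eligibility with every evaluated child eligible would overstate the result; hence the 60-90% range.

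**Conclusion.** The point holds as a cheap improvement. As worded, Hypothesis 1b compares arms within groups that arm can change, and no all-randomised analysis of initiation or duration is planned. Under the illustrative rates the eligible-only initiation difference moves 11 points in either direction with no direct navigator effect. In one scenario it has the opposite sign to the all-randomised difference of +11 to +16 points. With equal start rates of 90% it is zero, yet all randomised children show +16 to +24, so a navigator that works only by getting families evaluated would appear to do nothing in 1b. These sizes rest entirely on assumed evaluation, eligibility and start rates. That the groups form after randomisation rests on the documents; that eligibility is settled at the MDE is inferred. The Bayley-III primary endpoint is not touched.

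**What to change.** In SAP Hypothesis 1b:

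- Define eligibility for EI and state the denominator of each test.
- Add initiation of EI services by 12 months from randomisation in all randomised children, by logistic regression on arm, sex, age and site. Count as non-initiators the children whom parent report or EI program records show as not evaluated, not eligible or not started.
- Do not treat an empty Philadelphia record search as not started for a child known to have left the county, or for whom no release was signed. Children outside the county are referred elsewhere (Protocol 3.4), and moving away is anticipated (Protocol 3.4.2.1). Use parent report there, and otherwise the multiple imputation in Protocol 6.3.
- Add months in EI service between randomisation and 12 months in all randomised children, with zero for never-starters and the same 12-month window for every child. Say that this changes the SAP's duration definition for that analysis, because the SAP applies 12 months only when no discharge date is available. Use a method suited to many zeros, such as a difference in means with robust or bootstrap standard errors.
- Keep the eligible-only results as uptake once eligible, labelled as not protected by randomisation.
- If arm-level results have already been seen, label the added analyses accordingly.

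The cost is SAP wording and one analysis per outcome. Eligibility, initiation and service use are already collected from parents and the EI program (Protocol 3.1.1). The drawback is that the all-randomised effect combines referral completion, eligibility and starting, overlaps with Hypothesis 1a, and counts ineligible children as non-initiators, so both results should be reported together.

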## **3.2 Allocation to Treatment Groups and Blinding**

In this study, 360 eligible children will be randomized 1:1 to the FN or usual care consisting of routine Child Find procedures. We chose a randomized design, because it is most effective at guarding against bias and will ensure that patients in both arms are similar in observed and unobserved characteristics. The initial randomization will be stratified by practice site, child sex, and age group (0-<18 months old and 18-30 months old) to ensure

balance between groups. We will control post-hoc statistically for any imbalances that arise. Allocation concealment (blinding of the treatment assignment) will be implemented using sealed, opaque envelopes, along with stratification, and randomly permuted blocks of unequal sizes (to prevent providers and patients from manipulating the randomization). Treatment assignment will be done at the time of enrollment following informed consent and patients will be followed over time with measures related to EI referral completion, EI services completion, and patient engagement collected at baseline, 3, 6, 9, and 12 months as well as child developmental status around 12 months.

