## 5 STUDY EVALUATIONS AND MEASUREMENTS

### 5.1 Screening and Monitoring Evaluations and Measurements

#### 5.1.1 Medical Record Review

- Date of birth, Chart Review, History, Demographics
- Gestational age, sex, problem list, developmental assessments

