## 6.3 Control of Bias and Confounding

Randomization and allocation concealment are the primary means of avoiding bias. Analytic strategies will also be used to control for residual confounding: (1) Stratification will control for imbalance not controlled by design. (2) Additional potential confounders will be evaluated for any residual association with treatment and included in model as needed. (3) Post randomization effects: The primary source of bias will arise after randomization from dropout and loss to follow-up. To address this problem and avoid missing data, we shall implement the following measures: (a) incentives to each family to complete the study, (b) collection of multiple contact numbers and tracking of changes, and (c) contact all randomized participants, even if they do not continue with their clinical contacts. Baseline data collection will include questions about factors that predict potential dropout, such as current living situations and regularity of contact with health care providers. (4) Our analytic model for treatment effect will include not only potential confounders but also predictors of dropout, to be able to relax assumptions about the missing data process. (5) To investigate the possibly informative dropout (for reasons related to the intervention), we will implement sensitivity analyses (6) For missing values in any of the outcome measurement tools, we will implement formal methods of multiple imputation. (7) We shall account for all dropouts and check all baseline information in real time for both invalid values and missing items and then prompt the child's caregiver for any corrections or clarifications. Then, if any covariates remain missing, we shall implement multiple imputation. (8) Attenuation bias from non-compliance might also occur if the child remains

in the study but fails to adhere to all aspects of the intervention. To address this potential problem, and to estimate the effect of treatment in the presence of full compliance, we will implement the methods outlined by Small and colleagues and by Nagelkerke. However, the “as randomized” approach will remain the primary method for assessing statistical significance of the intervention.

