### 6.4.2 Analysis of Primary Outcomes of Interest

#### 6.4.2.1 *Specific Aim 1*

##### Primary outcomes

In order to determine the effectiveness of the Opening Doors to Early Intervention Program on child developmental status, our primary outcome for this aim is the Bayley-III cognitive subscale measured at 12 months follow-up. For our primary outcome, a linear mixed effects approach will be used to model differences in cognitive functioning between intervention groups accounting for clustering due to practice. Such an approach is advantageous for offering flexible means for accounting for potential issues that arise in randomized trials. For example, baseline patient characteristics that were not balanced across intervention groups by the randomization process can be accounted for through covariate level adjustment. Also, differential drop-out and loss to follow-up between groups can be accounted for by incorporating missing data methods such as multiple imputation.

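### The Aim 1 Bayley model prespecifies no prognostic covariate beyond sex, age and site, while the protocol lets further covariates in by observed imbalance; this forgoes precision and leaves the primary model open.

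*SAP*

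**What the plan says.** **SAP, Aim 1, Hypothesis 1c.** The Bayley analysis is "Logistic regressions to determine the difference in cognitive and language BSID III scores by arm, controlling for sex, age, and primary care site". No other covariate is named.

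**Protocol, primary model (6.4.2.1).** Here "a linear mixed effects approach will be used to model differences in cognitive functioning between intervention groups accounting for clustering due to practice". The section names no fixed covariate list.

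**Protocol, how further covariates enter.**
- 3.2: "We will control post-hoc statistically for any imbalances that arise".
- 6.3 item 2: "Additional potential confounders will be evaluated for any residual association with treatment and included in model as needed".
- 6.4.2.1: "baseline patient characteristics that were not balanced across intervention groups by the randomization process can be accounted for through covariate level adjustment".
- 6.3 item 4, a separate route that does not depend on imbalance: "Our analytic model for treatment effect will include not only potential confounders but also predictors of dropout". These predictors are not listed.

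**Baseline data.** The baseline visit records family income and maternal education (3.1.1) and StimQ (4.1.1). Chart review covers "Gestational age, sex, problem list, developmental assessments" (5.1.1). There is no baseline Bayley; Table 1 schedules it only at the final visit.

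**Use elsewhere.** SAP Aim 3 fits three Bayley models by arm, adding StimQ, SAHL or parent income one at a time. Protocol 6.4.2.3 also lists maternal education among the Aim 3 variables. Maternal education, gestational age and chart developmental assessments appear in no SAP model.

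**The concern.** Section 1.1 of the protocol links income and the home environment to developmental status and notes less enriched homes and lower literacy among poor families. Section 1.3.1.1 counts poverty and less enriching homes among the known risks for poor development. With no baseline Bayley, variables of this kind are the only source of prognostic adjustment beyond the stratifiers, and the Aim 1 model does not name them.

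The protocol's imbalance route does not fill the gap. Under randomisation, baseline imbalance arises by chance. Choosing covariates by their association with arm says nothing about whether they predict the outcome, so it brings no planned gain in precision. It also means that the primary model is settled only after the data have been inspected. The SAP's short list does not say that it replaces the protocol rule, so more than one primary model can be defended from the documents.

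**Working it through.** **1. The plan's own figure.** Section 6.5 gives 96% power for a 3-point difference with about 130 control and 170 intervention children. Its stated inputs are enrolment in EI of 50% against 80%, and a gain of 10 points (SD 1) for enrolled children. Alpha is not stated; two-sided 0.05 is assumed throughout.

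- Variance per arm if enrolment is the only source of spread: p × 1² + p(1 − p) × 10². Control: 0.5 + 25 = 25.5 (SD 5.05). Intervention: 0.8 + 16 = 16.8 (SD 4.10).
- SE = √(25.5/130 + 16.8/170) = 0.543; 3/0.543 = 5.52; power = Φ(5.52 − 1.96) = 99.98%.

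The 96% is therefore not reproduced. A common SD of 6.94 would give it: SE = 6.94 × √(1/130 + 1/170) = 0.809, and power = Φ(3/0.809 − 1.96) = 96%. The documents do not state that SD.

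**2. SD of the score.** None is given. Section 1.1 equates 0.43-0.75 SD with about 8-12 IQ points. Matching the ends gives 8/0.43 = 18.6 and 12/0.75 = 16.0. An SD of 15 is added as an assumption.

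**3. Effect of adjustment in a linear model.** With partial R² the share of outcome variance explained beyond sex, age and site:

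SE(adjusted) = SE × √(1 − R²); equivalent sample = 300/(1 − R²).

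| Partial R² (assumed) | SE falls by | 300 children behave like |
|---|---|---|
| 0.05 | 2.5% | 316 |
| 0.10 | 5.1% | 333 |
| 0.20 | 10.6% | 375 |
| 0.30 | 16.3% | 429 |

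Power for 3 points at 130/170 = Φ(3/SE − 1.96):

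| SD | SE at R² = 0 | R² 0 | 0.05 | 0.10 | 0.20 | 0.30 |
|---|---|---|---|---|---|---|
| 6.94 (back-solved from 96%) | 0.809 | 96.0% | 96.8% | 97.4% | 98.6% | 99.3% |
| 15 (assumed) | 1.748 | 40.4% | 42.1% | 44.0% | 48.4% | 53.7% |
| 16 (from 1.1) | 1.864 | 36.3% | 37.9% | 39.6% | 43.6% | 48.5% |
| 18.6 (from 1.1) | 2.167 | 28.2% | 29.5% | 30.8% | 34.0% | 38.0% |

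**4. The SAP's logistic wording.** The SAP gives no cut-point, so one was assumed midway between the arm means. In 1,000 simulated trials at SD 15 and R² 0.20, adjustment raised the SE of the log odds ratio from 0.235 to 0.253. The log odds ratio itself rose from 0.33 to 0.38, and power went from about 30% to 33%. The SE formula in step 3 therefore applies to the protocol's linear model only.

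**The case against.** The strongest reply is that sex, age and site are the randomisation stratifiers. A fixed model with those factors is prespecified and respectable, and the SAP itself contains no imbalance rule. Further covariates are then an optional gain in efficiency. This stands as far as validity goes. It does not settle which model is primary, because the SAP is silent on the protocol's three imbalance statements.

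A second reply is that the gain may be small. That also stands. Gestational age is restricted by eligibility (born after 35 weeks), and income probably varies less than usual in a sample aimed at poor families. At R² of 0.05 the SE falls only 2.5%.

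A reader might also infer more than the documents support:

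- **That the baseline data go unused.** They do not: StimQ, SAHL and income each enter a SAP Aim 3 Bayley model. The gap is in the Aim 1 model.
- **That imbalance is the protocol's only route to more covariates.** Item 4 of 6.3 also brings in predictors of dropout. Since these are unlisted, the model is still not fixed.
- **That the SAP's quoted model loses standard error.** It is written as logistic, and there adjustment raises the SE while modestly raising power.

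**Conclusion.** The point holds as a matter of efficiency and prespecification. The Aim 1 Bayley model names no prognostic covariate beyond sex, age and site, and the protocol leaves additions to observed imbalance or association with arm. It would go too far to call the randomised comparison biased by the omission, or to treat the loss as a known quantity.

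The size depends on two assumed inputs, the partial R² and the SD. Over R² of 0.10 to 0.30, the absolute power gain is about 4 to 13 percentage points at SD 15, and about 3 to 12 points at the SDs of 16 to 18.6 implied by section 1.1. If the stated 96% were right, the power gain would be at most about 3 points, although the interval would narrow by the same percentages. The case for fixing the model in advance does not depend on any of these values.

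**What to change.** 1. **SAP, Hypothesis 1c.** Settle the model family first: use the protocol's linear model for the cognitive composite, with arm, the stratifiers (site, sex, age group) and a short fixed list of family income category, maternal education and age-standardised StimQ.
2. **Availability.** StimQ is described for children from 5 months (5.1.2.1), while eligibility has no lower age limit. State a missing category or imputation for younger infants. Add gestational age and the chart developmental assessment only if they are available on a common scale for most children, and decide this before unblinding; 5.1.1 names no chart instrument.
3. **SAHL.** Do not use values collected after randomisation, which 4.1.1 and Table 1 allow.
4. **Protocol.** Replace the imbalance-based selection wording in all three places: 3.2, 6.3 item 2 and 6.4.2.1. List in advance any dropout predictors meant under 6.3 item 4.
5. **Missing covariates.** Handle them in line with 6.3 item 7, which specifies multiple imputation.

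The cost is wording in both documents, a few degrees of freedom out of about 300 children, and some imputation of baseline values. The core list needs no new data collection.
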